4.1.2 Preclinical and Clinical Trial Data

Refer to the Investigator's Brochure for Preclinical and Clinical data.

4.2 Rationale

4.2.1 Rationale for the Trial and Selected Subject Population

PD-1-targeted and VEGF-targeted therapies have separately shown survival benefit in subjects with advanced or metastatic renal cell carcinoma (mRCC). Mechanisms of synergy between VEGF and PD-1 inhibition have been proposed in the current literature. In this study, we will evaluate the efficacy of combining the PD-1 (pembrolizumab) and VEGF-targeted (cabozantinib) therapies in subjects with locally advanced, recurrent, or metastatic renal cell carcinoma.

The phase I dose escalation part will determine the maximum tolerated dose (MTD) and recommended phase 2 dose (RP2D) of the combination of pembrolizumab and cabozantinib.

The phase II dose expansion part will evaluate efficacy (as defined by objective response rate) of the combination given at the RP2D in mRCC subjects who are immunotherapy-naïve and also those who have previously received immunotherapy.

With the approval of nivolumab, we anticipate that many subjects will have received immunotherapy prior to study entry. Given the preclinical data for synergy with the combination of PD-1 and VEGF inhibition, we hypothesize that there will be subjects who did not previously respond to either PD-1 or VEGF-directed therapies alone, but who may respond to the combination.

The treatment of bone metastases and prevention of skeletal related events for mRCC is particularly challenging, and represents an unmet need for this cancer. There is preclinical evidence of a direct link between loss of von Hippel-Lindau and up-regulation of c-Met, as well as, evidence for high MET expression in bone metastases specimens.[17] High MET expression has been demonstrated both in RCC bone metastases and brain metastases.[13, 14] In addition to anti-angiogenic effects, cabozantinib has activity against MET. In this study, we will also explore the preliminary efficacy of targeting PD-1, VEGFR, and MET simultaneously with the combination of pembrolizumab and cabozantinib, in terms of time to

progression of bone metastasis or skeletal-related events.

4.2.2 Rationale for Dose Selection/Regimen/Modification

4.2.2.1 Rationale for Dose Selection of Pembrolizumab

An open-label Phase I trial (Protocol 001) is being conducted to evaluate the safety and clinical activity of single agent MK-3475 (pembrolizumab). The dose escalation portion of this trial evaluated three dose levels, 1 mg/kg, 3 mg/kg, and 10 mg/kg, administered every 2 weeks (Q2W) in subjects with advanced solid tumors. All three dose levels were well tolerated and no dose-limiting toxicities were observed. This first in human study of MK-3475 showed evidence of target engagement and objective evidence of tumor size reduction at all dose levels (1 mg/kg, 3 mg/kg and 10 mg/kg Q2W). No MTD was identified. 10.0 mg/kg Q2W, the highest dose tested in PN001, was the dose and schedule utilized in Cohorts A, B, C and D of this protocol to test for initial tumor activity. Recent data from other clinical studies within the MK-3475 program has shown that a lower dose of MK-3475 and a less frequent schedule may be sufficient for target engagement and clinical activity.

PK data analysis of MK-3475 administered Q2W and Q3W showed slow systemic clearance, limited volume of distribution, and a long half-life (refer to IB). Pharmacodynamic data (IL-2 release assay) suggested that peripheral target engagement is durable (>21 days). This early PK and pharmacodynamic data provides scientific rationale for testing a Q2W and Q3W dosing schedule.

A population pharmacokinetic analysis has been performed using serum concentration time data from 2,993 subjects. Within the resulting population PK model, clearance and volume parameters of MK-3475 were found to be dependent on body weight. The relationship between clearance and body weight, with an allometric exponent of 0.59, is within the range observed for other antibodies and would support both body weight normalized dosing or a fixed dose across all body weights. MK-3475 has been found to have a wide therapeutic range based on the melanoma indication. The differences in exposure for a 200 mg fixed dose regimen relative to a 2 mg/kg Q3W body weight based regimen are anticipated to remain well within the established exposure margins of 0.5 - 5.0 for MK-3475 in the melanoma indication. The approximation of similar efficacy and safety in melanoma at 10 mg/kg Q3W vs. the proposed dose regimen of 2 mg/kg Q3W (i.e. 5-fold higher dose and exposure). The population PK evaluation revealed that there was no significant impact of tumor burden on exposure. In addition, exposure was similar between the NSCLC and melanoma indications. Therefore, there are no anticipated changes in exposure between different indication settings.

The rationale for further exploration of 2 mg/kg and comparable doses of pembrolizumab in solid tumors is based on: 1) similar efficacy and safety of pembrolizumab when dosed at either

2 mg/kg or 10 mg/kg Q3W in melanoma subjects, 2) the flat exposure-response relationships of pembrolizumab for both efficacy and safety in the dose ranges of 2 mg/kg Q3W to 10 mg/kg Q3W, 3) the lack of effect of tumor burden or indication on distribution behavior of pembrolizumab (as assessed by the population PK model) and 4) the assumption that the dynamics of pembrolizumab target engagement will not vary meaningfully with tumor type.

The choice of the 200 mg Q3W as an appropriate dose for the switch to fixed dosing is based on simulations performed using the population PK model of pembrolizumab showing that the fixed dose of 200 mg every 3 weeks will provide exposures that 1) are optimally consistent with those obtained with the 2 mg/kg dose every 3 weeks, 2) will maintain individual subject exposures in the exposure range established in melanoma as associated with maximal efficacy response and 3) will maintain individual subjects exposure in the exposure range established in melanoma that are well tolerated and safe.

A fixed dose regimen will simplify the dosing regimen to be more convenient for physicians and to reduce potential for dosing errors. A fixed dosing scheme will also reduce complexity in the logistical chain at treatment facilities and reduce wastage.

The currently approved dose of pembrolizumab across multiple cancers is 200 mg IV every 3 weeks and this is the fixed dose used for this study.

4.2.2.2 Rationale for Dose Selection of Cabozantinib

Cabozantinib at a dose of 140 mg/day has been studied in 25 subjects with advanced RCC enrolled in a Phase 1 study (XL184-008).[18] Adverse events were the primary reason for treatment discontinuation in 24% of subjects and dose reduction was required in 80% (20/25) subjects. The median average daily dose was approximately 75.5 mg/day. Despite the dose reductions, 7 subjects (28%) had partial response and 13 subjects (52%) had stable disease, with a disease control rate of 80%. The median PFS was 12.9 months with a median follow-up of 14.7 months. In some subjects, there was evidence of clinical activity against bone metastatic lesions. Based on the long-term tolerability and clinical activity associated with doses of cabozantinib <140 mg in this and other trials, 60 mg daily was selected as the recommended starting dose in the phase III METEOR study of cabozantinib versus everolimus in advanced renal cell carcinoma.[15] This study showed a significant PFS benefit of cabozantinib over everolimus (median PFS 7.4 months vs. 3.8 months). Dose reductions occurred in 60% (197 of 331) subjects treated with cabozantinib and the median average daily dose was 9%.

In addition, results from a National Cancer Institute phase 1 trial of cabozantinib in combination with nivolumab in subjects with previously treated genitourinary tumors were presented during a poster discussion session (Abstract #774PD) at the European Society for

Medical Oncology (ESMO) 2016 Congress. Between July 2015 and September 2016, 24 subjects were accrued with metastatic urothelial carcinoma (n=7), urachal adenocarcinoma (n=4), squamous cell carcinoma of the bladder or urethra (n=3), germ cell tumor (n=4), castration-resistant prostate cancer (n=4), renal cell carcinoma (n=1), or trophoblastic tumor (n=1) and were treated in Part I of the study, which evaluated the combination of cabozantinib and nivolumab at four dose levels. The median number of prior systemic therapies was 3, and 10 subjects had received 4 or more prior therapies. The objective response rate was 43 percent among the 23 subjects who were evaluable for response, with one complete response and nine partial responses. Four of six subjects (67 percent) with urothelial cancer achieved a response. **The recommended doses for the ongoing expansion cohorts were determined to be cabozantinib at 40 mg daily and nivolumab at 3 mg/kg once every 2 weeks.**

Given the phase I and phase III cabozantinib dosing and toxicity data, and the recent results of the phase I cabozantinib plus nivolumab study identifying a RP2D of 40 mg/day for cabozantinib, we have chosen a starting dose of cabozantinib 40mg/day for this combination study of cabozantinib and pembrolizumab with standard 3+3 design. If none of the first 3, or if 1 or fewer of the first 6, DLT-evaluable subjects experiences a DLT, subjects will enroll in the next cohort with cabozantinib 60 mg/day. If 2 or more of the first 6 DLT-evaluable subjects in the 40 mg/day cohort experience a DLT, then subjects will enroll at one dose reduction with cabozantinib 20 mg/day.

4.2.3 Rationale for Endpoints

4.2.3.1 Efficacy Endpoints

The primary endpoint of this study is to determine the efficacy (defined as objective response rate, ORR) of the combination of pembrolizumab and cabozantinib.

The secondary endpoints of this study are to characterize dose limiting toxicities (DLTs), maximum tolerated dose (MTD), and recommended phase 2 dose (RP2D) for the combination of pembrolizumab and cabozantinib, as well as, other measures of efficacy including response by immune-mediated response criteria (irRECIST), progression-free survival, overall survival, time to progression of overall disease, time to progression of bone metastasis or skeletal-related events, clinical benefit rate [complete response (CR) + partial response (PR) + stable disease (SD), duration of response or disease stability, and duration on treatment in subjects treated beyond progression.

4.2.3.2 Biomarker Research

It is unclear whether PD-L1 expression is a predictive biomarker for response and survival with anti-PD-1 and PD-L1 agents in metastatic renal cell carcinoma. In the phase III nivolumab versus everolimus clinical trial in mRCC subjects (CheckMate 025) which

demonstrated overall survival advantage with nivolumab, PD-L1 expression did not correlate with probability of overall survival.[5] Therefore, evaluation of other potential immune biomarkers is necessary.

In this study, we will include mandatory archival tumor collection and optional pre- and posttreatment tumor biopsies for PD-L1 (QualTek Molecular Laboratories) and other immuneoncology testing which may include evaluation of other immune checkpoint markers, immune cell markers, and immune function markers. Biospecimens collected under this study will only be used for this research and will be destroyed upon completion of this study.

5.0 METHODOLOGY

5.1 Trial Participation Criteria

5.1.1 Subject Inclusion Criteria

In order to be eligible for participation in this trial, the subject must:

- 1. Subjects must have histological or cytological documentation of renal cell carcinoma.
- 2. Subjects must have locally advanced, recurrent, or metastatic disease.
- 3. Be willing and able to provide written informed consent/assent for the trial.
- 4. Stated willingness to comply with all study procedures and be available for the duration of the trial.
- 5. Be \geq 18 years of age on day of signing informed consent.
- 6. Have measurable or evaluable disease based on RECIST 1.1.
- 7. Recovery to baseline or \leq Grade 1 CTCAE v.4.0 from toxicities related to any prior treatments, unless AE(s) are clinically non-significant and/or stable on supportive therapy.
- 8. Confirmed availability of representative archival tumor specimens in paraffin blocks (preferred) or ≥ 10 unstained slides, with an associated pathology report.

Acceptable samples include core needle biopsies for deep tumor tissue or excisional, incisional, or punch biopsies for cutaneous, subcutaneous, or mucosal lesions.

Tumor tissue from bone metastases is not evaluable for PD-L1 expression and

is therefore not acceptable.

A subject with insufficient or unavailable archival tissue may be eligible, upon discussion with the Principal Investigator, if the subject is willing to consent to undergo a pretreatment core, punch, or excisional/incisional biopsy sample collection of the tumor.

9. Have a performance status of 0 or 1 on the ECOG Performance Scale.

10. Demonstrate adequate organ function as defined in Table 1.

| System | Laboratory Value | | |
|---|---|--|--|
| Hematological | | | |
| Absolute neutrophil count (ANC) | ≥1,500 /mcL | | |
| Platelets | ≥100,000 / mcL | | |
| Hemoglobin | \geq 9 g/dL or \geq 5.6 mmol/L without transfusion or EPO dependency (within 7 days of assessment) | | |
| Renal | | | |
| Serum creatinine OR | \leq 1.5 X upper limit of normal (ULN) OR | | |
| Measured or calculated ^a creatinine | | | |
| clearance | \geq 60 mL/min for subject with creatinine levels > 1.5 X | | |
| (GFR can also be used in place of | institutional ULN | | |
| creatinine or CrCl) | — | | |
| Urine protein | \leq 1+ or \leq 30 mg/dL OR urine protein/creatinine ratio \leq 1 | | |
| Hepatic | | | |
| Serum total bilirubin | ≤ 1.5 X ULN OR | | |
| | Direct bilirubin \leq ULN for subjects with total bilirubin levels $>$ | | |
| | 1.5 ULN. For subjects with Gilbert's disease $\leq 3 \text{ mg/dL}$. | | |
| AST (SCOT) and ALT (SCDT) | \leq 2.5 X ULN OR | | |
| AST (SOOT) and ALT (SOFT) | \leq 5 X ULN for subjects with liver metastases | | |
| Albumin | $\geq 2.5 \text{ mg/dL}$ | | |
| Coagulation | | | |
| International Normalized Ratio (INR) or Prothrombin Time (PT) | \leq 1.5 X ULN unless subject is receiving anticoagulant therapy as long as PT or PTT is within therapeutic range of intended use of anticoagulants | | |
| Activated Partial Thromboplastin Time (aPTT) | \leq 1.5 X ULN unless subject is receiving anticoagulant therapy as long as PT or PTT is within therapeutic range of intended use of anticoagulants | | |
| Activated Partial Thromboplastin Time (aPTT) ^a Creatinine clearance should be calculated | as long as PT or PTT is within therapeutic range of intended of anticoagulants per institutional standard. | | |

Table 1: Adequate Organ Function Laboratory Values

11. Female participants of childbearing potential should have a negative urine or serum pregnancy within 72 hours prior to receiving the first dose of study medication and should not be breastfeeding. If the urine test is positive or cannot be confirmed as negative, a serum pregnancy test will be required.

12. Female subjects of childbearing potential must be willing to use an adequate method of contraception as outlined in Section 5.5.2 – Contraception, for the course of the study through 120 days after the last dose of study medication.

Note: Abstinence is acceptable if this is the usual lifestyle and preferred contraception for the participant.

13. Male participants of childbearing potential must agree to use an adequate method of contraception as outlined in Section 5.5.2 – Contraception, starting with the first dose of study therapy through 120 days after the last dose of study therapy and refrain from donating sperm during this period.

Note: Abstinence is acceptable if this is the usual lifestyle and preferred contraception for the subject.

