ii. Uncontrolled hypertension defined as sustained BP > 150 mm Hg systolic or > 100 mm Hg diastolic despite optimal antihypertensive treatment.

iii. Stroke (including TIA), myocardial infarction, or other ischemic event, or thromboembolic event (e.g., deep venous thrombosis, pulmonary embolism) within 3 months before randomization.

b. Gastrointestinal (GI) disorders including those associated with a high risk of perforation or fistula formation:

i. Tumors invading the GI-tract, active peptic ulcer disease, inflammatory bowel disease, diverticulitis, cholecystitis, symptomatic cholangitis or appendicitis, acute pancreatitis or acute obstruction of the pancreatic or biliary duct, or gastric outlet obstruction.

ii. Abdominal fistula, gastrointestinal perforation, bowel obstruction, or intra-abdominal abscess within 6 months before randomization. Complete healing of an intra-abdominal abscess must be confirmed before study initiation.

c. Has clinically significant hematuria, hematemesis, or hemoptysis of > 0.5 teaspoon within 3 months before randomization.

- d. Known endobronchial disease manifestation. Patients with suspected endobronchial disease on imaging who have no evidence of endobronchial disease on bronchoscopy are allowed. Patients with treated endobronchial disease are also allowed provided they are stable.
- e. Lesions invading major pulmonary blood vessels.
- 20. Has a history or current evidence of any condition, therapy, or laboratory abnormality that might confound the results of the trial, interfere with the subject's participation for the full duration of the trial, or is not in the best interest of the subject to participate, in the opinion of the treating investigator.
- 21. Has known psychiatric or substance abuse disorders that would interfere with cooperation with the requirements of the trial.
- 22. Is pregnant or breastfeeding, or expecting to conceive or father children within the projected duration of the trial, starting with the pre-screening or screening visit through 120 days after the last dose of trial treatment.
- 23. Has an inability to swallow tablets or capsules.
- 24. Has a previously identified allergy or hypersensitivity to components of the study treatment formulations.
- 25. Has a known history of Human Immunodeficiency Virus (HIV) (HIV 1/2 antibodies).
- 26. Has known active Hepatitis B (e.g., HBsAg reactive) or Hepatitis C (e.g., HCV RNA [qualitative] is detected).

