5.2.1.3.2 Pembrolizumab Second Course

The participant's initial course of treatment with pembrolizumab will be the First Course, and in the absence of disease progression may be administered for up to 35 cycles. After the First Course, all participants who stop pembrolizumab after 35 cycles with SD or better may be eligible for up to an additional 17 cycles (approximately 1 year) of pembrolizumab treatment if they progress after stopping pembrolizumab from the initial treatment phase.

This retreatment is termed the Second Course phase and is only available if the participant continues on cabozantinib monotherapy and remains on study after completing the First Course of pembrolizumab and meets the following conditions:

Either

- Stopped initial study intervention after attaining an investigator-determined confirmed CR based on RECIST 1.1, and
 - Was treated with at least 8 cycles of pembrolizumab before discontinuing treatment, and
 - Received at least 2 treatments with pembrolizumab beyond the date when the initial CR was declared

OR

• Had SD, PR, or CR and stopped pembrolizumab after completion of 35 administrations (approximately 2 years) of study intervention for reasons other than disease progression or intolerability

AND

- Experienced an investigator-determined radiographic disease progression by RECIST 1.1 after stopping initial treatment, and
 - The participant meets all of the safety parameters listed in the inclusion criteria and none of the safety parameters listed in the exclusion criteria, and
 - The patient remained on study while still continuing to dose with cabozantinib monotherapy after stopping initial pembrolizumab treatment (First Course).

Additionally, the treating physician must determine at the time of progression after stopping initial treatment that continuing cabozantinib and resuming pembrolizumab is the best treatment course for the patient.

An objective response or disease progression that occurs during the Second Course Phase for a participant will not be counted as an event for the primary analysis of either endpoint in this study.

Participants who have experienced an initial disease progression by RECIST 1.1 and have an iSD, iPR,or iCR per iRECIST after completion of 35 administrations of study intervention for reasons other than disease progression or intolerability may be considered for the Second Course Phase after consultation with the Sponsor-Investigator.

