5.2.1.4 Cabozantinib

See Sections 2.1.1 to 2.1.6 for dosing of cabozantinib during the DLT assessment window in Phase I dose escalation.

Dose modification criteria for cabozantinib outside the DLT assessment window and in the dose expansion stage are shown in Table 4. Dose reductions and/or interruptions should be implemented for unacceptable toxicity. Dose modifications or interruptions may also occur in the setting of lower grade toxicity than defined in Table 4, if the investigator feels it is in the interest of the subject's safety and will optimize drug tolerability.

| CTCAE v4.0 Grade | Recommended Guidelines for Management |
|---|---|
| Grade 1 AEs | Add supportive care as indicated. |
| | Continue cabozantinib treatment at current dose level if AE is manageable and tolerable. |
| Grade 2 AEs which are tolerable and are easily managed | Continue cabozantinib treatment at current dose level with supportive care. |
| Grade 2 AEs which are intolerable and cannot be adequately managed | At the discretion of the investigator, cabozantinib should be dose reduced or interrupted until symptoms become more tolerable or are better managed. |
| Grade 3 AEs (except clinically non-relevant laboratory abnormalities) | Hold cabozantinib treatment and optimize supportive care. |
| | Once AE improves to \leq Grade 2 and is tolerable and manageable, resume cabozantinib: |
| | • At same dose if first occurrence of Grade 3 AE despite optimal supportive care. |
| | • At one dose reduction (decrease by 20mg/day) if second occurrence of Grade 3 AE despite optimal supportive care. |
| | Permanently discontinue cabozantinib if third occurrence of Grade 3 AE despite optimal supportive care. |
| Grade 4 AEs (except clinically non-relevant laboratory abnormalities) | Hold cabozantinib treatment immediately. |
| | Discontinue cabozantinib permanently UNLESS the following criteria are met: Subject is deriving clear clinical benefit as determined by the investigator and agreed by the Principal Investigator. |
| | • Toxicity can be managed with a dose reduction following recovery to Grade 1 (or baseline) and optimal medical care. |

Table 4: Dose Modification Guidelines for Cabozantinib Drug-Related Adverse Events

Cabozantinib should be permanently discontinued for any of the following:

- Development of visceral perforation or fistula formation
- Severe hemorrhage
- Serious arterial thromboembolic event (e.g., myocardial infarction, cerebral infarction)

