- Nephrotic syndrome (e.g. proteinuria > 2 grams/day on 24 hour urine or urine protein creatinine ratio >3.5 AND serum albumin < 2 mg/dL AND edema)
- Malignant hypertension, hypertensive crisis, persistent uncontrolled hypertension despite optimal medical management.
- Osteonecrosis of the jaw
- Reversible posterior leukoencephalopathy syndrome

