- Cabozantinib treatment should be discontinued in subjects who develop an acute myocardial infarction or any other clinically relevant arterial thromboembolic complication.

• Proteinuria:

○ If urinalysis shows proteinuria \ge 3+, obtain spot urine protein creatinine ratio.

| Severity of Proteinuria (UPC Ratio) | Action to be Taken | | | | |
|---|---|--|--|--|--|
| UPC Ratio ≤ 1 | No change in cabozantinib treatment or monitoring. | | | | |
| UPC Ratio > 1 to < 3.5 | No change in cabozantinib treatment required. | | | | |
| | Consider confirming with a 24-hour protein assessment within 7 days. Repeat UPCR within 7 days and once per week. If UPCR < 1 on 2 consecutive readings, UPCR monitoring can revert to protocol-specific times. | | | | |
| UPC Ratio ≥ 3.5 | Hold cabozantinib treatment pending repeat UPCR within 7 days and/or 24-hour urine protein. | | | | |
| | If \geq 3.5 on repeat UPCR, continue to hold cabozantinib treatment and check UPCR every 7 days. If UPCR decreases to < 2, restart cabozantinib treatment at a reduced dose and monitoring of urine protein/creatinine should continue weekly until the UPCR decreases to < 1. | | | | |
| Nephrotic syndrome (e.g. proteinuria > 2 grams/day on 24 hour urine or urine protein creatinine ratio >3.5 AND serum albumin < 2 mg/dL AND edema) | Discontinue cabozantinib treatment. | | | | |

Table 9: Management of Cabozantinib-Related Proteinuria

• Hypophosphatemia:

- Serum phosphorus should be monitored frequently while receiving cabozantinib.
- Mild to moderate hypophosphatemia should be managed by oral replacement including food that are high in phosphate (diary items, meats, beans) and/or oral phosphate supplements according to standard clinical practice guidelines.

• Thyroid Function Disorders:

- Changes in thyroid function tests (TFTs) and hypothyroidism have been reported with cabozantinib and other tyrosine kinase inhibitor treatment as a result of altered thyroid hormone regulation.
- Management of thyroid dysfunction (e.g., symptomatic hypothyroidism) should follow accepted clinical practice guidelines.

• Hemorrhagic Events:

• Discontinue cabozantinib treatment in subjects who have been diagnosed with a severe bleeding complication.

• GI Perforation/Fistula and Non-GI Fistula Formation:

- Carefully monitor for episodes of abdominal pain, especially in subjects with known risk factors for developing GI perforation/fistula or non-GI fistula, to allow for early diagnosis.

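### Table 1 prints the binding albumin entry limit in mg/dL, presumably for g/dL, so as written it excludes no one

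*Combined protocol and SAP*

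**What the plan says.** Inclusion criterion 10 in section 5.1.1 requires every subject to "Demonstrate adequate organ function as defined in Table 1". In the hepatic block of that table the albumin row reads "Albumin | $\geq 2.5 \text{ mg/dL". The hemoglobin row of the same table is in g/dL.

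Albumin limits appear in two more places, both describing nephrotic syndrome as a reason to stop cabozantinib for good: the permanent-discontinuation list in section 5.2.1.4, and the last row of Table 9 in section 5.4.2. Each gives an example, introduced by 'e.g.', that combines heavy proteinuria with "serum albumin < 2 mg/dL AND edema".

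Table 10 in section 7.1.3 lists albumin among the chemistry tests but gives no unit. No section states an albumin limit in g/dL or corrects the unit in Table 1.

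**The concern.** An eligibility limit is useful only if some patients can fail it. Serum albumin is a matter of grams, not milligrams, per decilitre, so a floor of 2.5 mg/dL cannot be failed. Table 1 is operative text: a site that copies the number and unit into an eligibility checklist has an albumin line that everyone passes. A site that silently reads g/dL applies a different criterion from the one approved. Two careful sites could therefore decide differently on the same patient. A monitor checking compliance with the approved protocol (section 10.6.2) could not cite the text against the site that enrolled.

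In the nephrotic-syndrome example the same slip works the other way. The entry limit is always met, while the albumin part of the example never is.

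**Working it through.** **Inputs from the documents.** Entry minimum 2.5 mg/dL (Table 1). Nephrotic-syndrome example below 2 mg/dL (section 5.2.1.4 and Table 9), beside proteinuria above 2 grams/day.

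**Assumed inputs.** The documents give no albumin values for patients, so each limit is tried on 1.0 to 5.0 g/dL. The conclusion on the entry limit holds for any albumin above 0.0025 g/dL.

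**Conversion.** 1 g/dL = 1,000 mg/dL.

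- 2.5 mg/dL ÷ 1,000 = 0.0025 g/dL
- 2 mg/dL ÷ 1,000 = 0.002 g/dL

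**Each reading of the limits applied.**

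| Albumin, g/dL | Same, mg/dL | Entry as printed (≥ 2.5 mg/dL) | Entry in g/dL (≥ 2.5) | Example as printed (< 2 mg/dL) | Example in g/dL (< 2) |
|---|---|---|---|---|---|
| 1.0 | 1,000 | pass | fail | not met | met |
| 1.5 | 1,500 | pass | fail | not met | met |
| 2.0 | 2,000 | pass | fail | not met | not met |
| 2.5 | 2,500 | pass | pass | not met | not met |
| 3.5 | 3,500 | pass | pass | not met | not met |
| 5.0 | 5,000 | pass | pass | not met | not met |

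As printed, every value passes entry, by a factor of 1,000 ÷ 2.5 = 400 up to 5,000 ÷ 2.5 = 2,000. No value meets the example's albumin part. With g/dL, both limits separate patients.

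**Could mg/dL be intended?** Assume a plasma volume of 25 to 35 dL. At 2 mg/dL the whole plasma would hold 25 × 0.002 = 0.05 g to 35 × 0.002 = 0.07 g of albumin. The same example has more than 2 g of protein lost in the urine each day, and the two cannot be reconciled. The unit also recurs in three separate places, so a fault in reading one table cell is an unlikely explanation.

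**Does any statistical figure depend on it?** No. The Simon figures in section 8.2.5 use only the stage sizes (20 and 38), the boundaries (2 and 12) and the response rates (0.20 and 0.50). From these, recomputation gives early termination 0.206, expected size 34.29, type I error 0.029 and power 0.983. These match the plan's figures, and albumin is not an input to any of them.

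**The case against.** The strongest reply is that this is a self-evident misprint that clinical staff would read as g/dL without noticing. For harm to follow, someone would have to convert a reported albumin to mg/dL to satisfy an impossible limit. That is probably right, and it is why the effect is small. It does not make the text correct: a site must depart from the written criterion to apply the intended one.

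A second reply is that other safeguards cover most of the risk, and this also largely stands:

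- Table 1 limits urine protein by dipstick or by "urine protein/creatinine ratio", and limits bilirubin, AST/ALT and INR.
- ECOG status must be 0 or 1.
- Exclusion 20 lets the investigator exclude for a "condition, therapy, or laboratory abnormality that might confound the results of the trial".
- The chemistry panel is repeated each cycle (section 6.0), and results must be acceptable before each dose (section 7.1.3).
- On treatment, section 5.2.1.4 adds that "Dose modifications or interruptions may also occur in the setting of lower grade toxicity than defined in Table 4".

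None of these is a numeric albumin floor at entry.

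Three stronger readings are tempting, and the documents do not support them.

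1. *A reader might infer a number of wrongly enrolled subjects.* That needs the share of candidates with albumin below 2.5 g/dL, which the documents do not give, and it needs staff to apply the printed unit. The planned 55 would also be the wrong base, since it allows for screen failures. The evaluable maximum is 9 + 38 = 47, or fewer if phase I subjects at the recommended dose count in stage I.
2. *A reader might infer that the faulty limit also governs retreatment.* Section 5.2.1.3.2 does say "The participant meets all of the safety parameters listed in the inclusion criteria", but it does not define which parameters those are, so reuse of the albumin limit is not established.
3. *A reader might infer that the nephrotic-syndrome stopping rule is disabled.* The wording is only an example, and the trigger is the clinical diagnosis. The example can also be read so that 24-hour proteinuria suffices alone. Separately, at a UPC ratio of 3.5 or more Table 9 says "Hold cabozantinib treatment pending repeat UPCR within 7 days" and/or a 24-hour urine protein, whatever the albumin.

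**Conclusion.** The point holds as a unit error in a binding entry criterion. The printed limit is 1,000 times below the presumed one and excludes no one, so the protocol as written has no working numeric albumin floor at entry. The same error in the two nephrotic-syndrome examples makes their albumin part impossible to meet, but those passages only illustrate.

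That g/dL was intended is an inference from the numbers and from the internal check against proteinuria; the documents do not say so. Whether 2.5 and 2 are the right values is for the clinical team. This is a minor correction for patient selection and safety wording, with no bearing on the primary endpoint or its analysis.

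**What to change.** At the next amendment, change mg/dL to g/dL for albumin in Table 1 (section 5.1.1), in the permanent-discontinuation list of section 5.2.1.4, and in the nephrotic-syndrome row of Table 9 (section 5.4.2). The clinical team should confirm 2.5 g/dL and 2 g/dL as the intended values. Any eligibility checklist built from Table 1 should carry the same correction.

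The cost is one unit in three places. No design, sample size or analysis changes.
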